5.3.1. Inclusion criteria

Patients must meet the following inclusion criteria in order to be eligible for inclusion in the study:

- Patient has a minimum of 1-year post-operative follow-up data available, or complete data to death

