2. SYNOPSIS

Title:	A Retrospective, Observational, Multicenter, Study to Collect Clinical Safety and Performance data on POLYTHESE® vascular prostheses
Study Population :	Subjects who did receive POLYTHESE® at least one year ago for replacement or bypass of pathological arteries. 3 main sub-populations will be studied depending on location of surgery (thoracic or abdominal and peripheral), but data will be collected for all subjects who did receive POLYTHESE® vascular prosthesis.
Study Design:	Multi-center retrospective case series
Study Type:	PMCF
Number of subjects:	Data from a minimum of 300 subjects will be evaluated. A minimum of 200 subjects will be evaluated for thoracic location of surgery.
Follow-up	At least 1-year follow-up after surgery until a maximum of 5 years.
Study Product:	Any POLYTHESE® vascular prosthesis of following ranges: 
 - POLYTHESE® IC - POLYTHESE® ICT - POLYTHESE® IC-3GL
Intended use:	POLYTHESE® vascular prostheses are indicated for replacement or bypass of arteries presenting aneurysm or arterial disease. Their indication is restricted to thoracic, abdominal and peripheral surgery not involving the crossing of the knee flexion crease.
Objectives:	
 • Describing safety and performance of POLYTHESE® throughout its expected lifetime
Performance primary endpoint:	Primary patency rate at 1 year after surgery using POLYTHESE®
Safety Primary endpoints:	
 • Mortality rate at 30 days after surgery using POLYTHESE®
Performance secondary endpoints:	
 • Procedural success rate • Primary patency rate at 30 days and 6 months after surgery using POLYTHESE® • Primary assisted patency rate at 30 days, 6 months and 1 year after surgery using POLYTHESE® • Secondary patency rate at 30 days, 6 months and 1 year after surgery using POLYTHESE®

PROTOCOL	2021-PT-01
TITLE:	Safety and Performance of POLYTHESE® vascular prosthesis
EFFECTIVE DATE:	1 July 2021
	
 • Device failure during procedure or at discharge, at 30 days, 6 months and 1 year after surgery using POLYTHESE®

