Safety secondary endpoints	
 • Mortality rate during procedure or at discharge, at 6 months and 1 year after surgery using POLYTHESE® • Limb salvage rate at 30 days, 6 months and 1 year after surgery using POLYTHESE® • Adverse event during procedure or at discharge, at 30 days, 6 months and 1 year after surgery using POLYTHESE®
Exploratory endpoints	
 • After 1 year until the end of follow-up (5 years) using POLYTHESE®: 
 ○ Primary patency ○ Primary assisted patency ○ Secondary patency ○ Device failure ○ Mortality ○ Limb salvage ○ Adverse events ○ Identify possible systematic misuse or off-label use of POLYTHESE®, with a view to verifying that the intended clinical purpose is correct.
Inclusion criteria	Subjects who did receive POLYTHESE® (IC, ICT, IC-3GL) at least one year ago for replacement or bypass of arteries presenting aneurysm or arterial disease
Exclusion criteria	Patients who have objected to the collect of their data
Duration of the data collect:	6 months from first site operational to collect data until data delivery
Data to be collected (as far as available)	
 • Identification and demographic data 
 ○ Patient characteristics ○ Indication and location of surgery ○ Patients demographics and risk factors ○ Summary of previous cardiovascular interventions ○ Relevant medications ○ Diagnosis • Operative data 
 ○ Date of procedure

PROTOCOL	2021-PT-01
TITLE:	Safety and Performance of POLYTHESE® vascular prosthesis
EFFECTIVE DATE:	1 July 2021

- Identification data for the prosthesis
- Information related to the surgical procedure
- Relevant medication
- Assessment of prosthesis function and mode of assessment if available
- Device failure modes and documented adverse operative events

- **Post-operative data (follow-up)**

- Date of follow-up visits
- Summary of vascular interventions, including minimally invasive procedures
- Clinical evaluation
- Relevant medications
- Device failure modes and documented adverse events

- **Any documented adverse events data (as far as available)**

- Type of event, date of occurrence, severity, management, outcome
- Any Documentation of probable causative factors (e.g. caused by the prosthesis, patient factors, technical factors)

Timepoints of collected data	- During procedure and at discharge (7-14 days)

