5.3. Subjects

The participating hospitals will screen all potential subjects and will select those who are appropriate for study inclusion, i.e. subjects implanted with POLYTHESE® for at least one year, or with complete data to death. As the study explores real world data, there is no exclusion criteria for subjects and all subjects with POLYTHESE® implanted for at least one year and have not objected to the collect of their data will be included in the study.

All data will be retrieved from medical charts for each patient from time of surgery (considered as index date) until a maximum of 5 years after surgery.

Data from a minimum of 300 from 3 to 8 different sites in France will be evaluated. A minimum of 200 subjects with thoracic location of surgery will be evaluated.

Not more than 50% of study total enrolled subjects shall pertain to one unique centre.

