5.3.2. Exclusion criteria

There are no exclusion criteria apart from patients who have objected to the collect of their data.

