8. STATISTICAL CONSIDERATIONS

8.1. Statistical design, method and analytical procedures

All patients participating in the study who met the eligibility criteria will be included in the study population.

A descriptive analysis with clinical characteristics of all patients included in the study will be performed at the index date.

Exploratory analyses will be conducted globally and stratified by sub-populations. Sub-populations will be defined according to the three main areas of surgery:

- Thoracic
 - o Ascending aorta and/or aortic arch and/or descending thoracic aorta and/or thoraco-abdominal aorta
- Abdominal
 - o Aorto-aortic and/or aorto-iliac and/or aorto-femoral repair
- Peripheral

PROTOCOL	2021-PT-01
TITLE:	Safety and Performance of POLYTHESE® vascular prosthesis
EFFECTIVE DATE:	1 July 2021

- Peripheral artery repair and extra anatomic bypasses not crossing the knee flexion crease

Since no hypotheses will be tested, study objectives will be addressed using descriptive statistics only. Given the real-world nature of the data, the use of multiple imputation methods for missing data would introduce bias as missing data cannot be considered completely at random (MCAR) or at random (MAR). Variables will not be imputed, with the exception of dates in which the exact day is missing: the missing day will be replaced by the middle day of the month.

Continuous variables will be described with number of patients with valid / missing observations, mean and its 95% confidence interval (95%CI), standard deviation (SD), median, 25 and 75 percentiles (P25 and P75, respectively), minimum and maximum. For non-normally distributed continuous variables geometric mean and its 95%CI will be reported too.

For categorical variables counts and percentages per category will be presented. Missing observations (including invalid or outlier observations) will be tabulated as a separate category. The calculation of proportions will not include the missing/invalid category in the denominators.

P-values will be presented in the summary tables, in association with the descriptive statistics. In addition, 95% confidence intervals (95%CI) will be presented when considered convenient or relevant. Results will be graphically represented when appropriate to make interpretation easier.

The two-sided level of significance will be set at 0.05 for all the statistical tests performed.

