13. INFORMED CONSENT PROCESS

An information letter explaining the purpose of this PMCF study will be sent to patients who meet the inclusion criteria. In accordance with the MR-004, the collection of data of patients who have not objected this collect will be initiated.

The completion of this process will be recorded in study documentation.

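### Section 5.3.1 makes entry depend on 1 year of follow-up data, which the synopsis inclusion row and section 5.3 do not, so the 30-day mortality denominator depends on which rule is followed

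*Protocol*

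**What the plan says.** Section 5.3.1 gives a single mandatory inclusion criterion: "Patient has a minimum of 1-year post-operative follow-up data available, or complete data to death". The synopsis follow-up row leans the same way: "At least 1-year follow-up after surgery until a maximum of 5 years".

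Two places set a test of elapsed time only. The synopsis inclusion row takes "Subjects who did receive POLYTHESE® (IC, ICT, IC-3GL) at least one year ago", together with a limit on the indication. Section 5.3 says that "all subjects with POLYTHESE® implanted for at least one year and have not objected to the collect of their data will be included".

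Another sentence of 5.3 describes suitable patients as "subjects implanted with POLYTHESE® for at least one year, or with complete data to death". It shares the death alternative with 5.3.1 but states no condition on follow-up data.

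Three further places decide the consequence:

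- Section 8.1 (statistical design): "All patients participating in the study who met the eligibility criteria will be included in the study population".
- Section 9.4: proportions use non-missing observations, without imputation.
- Section 13: "An information letter explaining the purpose of this PMCF study will be sent to patients who meet the inclusion criteria".

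The primary safety endpoint is 30-day mortality and the primary performance endpoint is 1-year primary patency (synopsis and section 7).

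**The concern.** Time since implantation and availability of a year of data are different tests. Take a patient operated on two years ago, seen alive at day 60 and never again. Section 5.3 says that this patient will be included if there is no objection; section 5.3.1 says that the patient cannot be.

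The condition suits 1-year patency. As an entry rule, however, it also governs 30-day mortality, and makes membership of that denominator depend on what happens after day 30. The patient's day-30 status is known, so the loss comes from the entry rule and not from missing data. A SAP cannot repair this, because patients refused at entry are never extracted. Since the information letter follows the inclusion criteria, the same rule decides who is informed.

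**Working it through.** **No figure to reproduce.** The minimum of 300 subjects (200 thoracic) rests on feasibility. The protocol states no expected 30-day mortality, 1-year mortality or loss rate. All rates below are assumptions.

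**Notation**

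- m30, m1y: true mortality by day 30 and by 1 year.
- c1, c2: shares of deaths by day 30, and from day 31 to 1 year, that have complete data.
- f: share of 1-year survivors with a full year of data.
- e: share of the lost 1-year survivors whose records stop before day 30.

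**Formulas**

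- Rate under 5.3.1: R1 = c1·m30 / [c1·m30 + c2·(m1y − m30) + f·(1 − m1y)].
- Rate under the elapsed-time rule, on patients with known day-30 status: R2 = m30 / [1 − e·(1 − f)·(1 − m1y)]. This takes day-30 status as known for everyone who died within the year.
- Effect of 5.3.1 = R1 − R2. The comparison has to be with R2 and not with m30, because survivors lost before day 30 go uncounted under either rule (section 9.4).

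**Base case: m30 = 5%, m1y = 10%, c1 = c2 = 1**

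- f = 0.9: R1 = 0.05/(0.05 + 0.05 + 0.81) = 0.05/0.91 = 5.49%.
- f = 0.7: R1 = 0.05/(0.05 + 0.05 + 0.63) = 0.05/0.73 = 6.85%.

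| Losses before day 30 (e) | R2, f = 0.9 | Effect | R2, f = 0.7 | Effect |
|---|---|---|---|---|
| none | 0.05/1 = 5.00% | 0.49 | 0.05/1 = 5.00% | 1.85 |
| half | 0.05/0.955 = 5.24% | 0.26 | 0.05/0.865 = 5.78% | 1.07 |
| all | 0.05/0.91 = 5.49% | 0 | 0.05/0.73 = 6.85% | 0 |

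Effects are in percentage points. Unrounded, the largest is 6.849 − 5 = 1.849, or 1.8 to one decimal.

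**Other mortality levels, c1 = c2 = 1** (effect with no loss before day 30, then with half)

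- 3% and 6%: f = 0.9 gives R1 = 0.03/0.906 = 3.31%, effect 0.3 then 0.2. f = 0.7 gives 0.03/0.718 = 4.18%, effect 1.2 then 0.7.
- 10% and 15%: f = 0.9 gives R1 = 0.10/0.915 = 10.93%, effect 0.9 then 0.5. f = 0.7 gives 0.10/0.745 = 13.42%, effect 3.4 then 2.0.

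**Direction.** R1 exceeds R2 only if c1 exceeds the retained share of patients known to be alive at day 30. In the base case with c2 = 1 and e = 0, that share is 0.86/0.95 = 0.905 (f = 0.9) or 0.68/0.95 = 0.716 (f = 0.7). With e = one half it is 0.86/0.905 = 0.950 or 0.68/0.815 = 0.834. If c1 = 0.7, R1 = 0.035/0.895 = 3.9% or 0.035/0.715 = 4.9%, both below the true 5%.

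**Against sampling error.** The half-width 1.96·√[p(1 − p)/n] at p = 5% is 2.5 points for n = 300 and 3.0 for n = 200. At p = 10% it is 3.4 and 4.2.

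**The case against.** There is a fair case that the conflict is narrow. Section 5.3.1 is the only list worded as mandatory, and the synopsis follow-up row agrees with it. The death alternative in 5.3 can be read as shorthand for 5.3.1, since for anyone implanted over a year ago it otherwise adds nothing. This stands as far as it goes, but the synopsis inclusion row and the all-subjects sentence of 5.3 remain, and neither can be squared with 5.3.1.

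A reader might count section 5.3.2 as a further contradiction: "There are no exclusion criteria apart from patients who have objected to the collect of their data". It is not one. Having no exclusion criteria is compatible with having an inclusion criterion. Nor do the documents show that sites would in fact apply different rules; they only leave room for it.

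The size is also open to challenge. Nothing is tested, the protocol sets no 30-day mortality threshold that a shift could cross, and in the base case the error counts against the device. The base-case shifts lie below the confidence-interval half-width. All of that stands and limits the severity. It does not remove the point, because a confidence interval does not reflect selection at entry.

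Lastly, one could keep 5.3.1, align the other passages to it, and report the patients screened out with their day-30 status. That would end the contradiction. But the 30-day rate would still rest on a selected group, and section 13 describes an information step only for patients who meet the criteria. The restriction is not needed for 1-year patency either, as section 9.4 already accepts missing endpoints.

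**Conclusion.** The contradiction is in the current text and depends on no assumption. Following 5.3.1 makes the primary safety endpoint depend on follow-up after day 30.

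The size is assumption-driven. At 5% and 10% mortality with all deaths retained, 5.3.1 raises the reported rate by at most 0.5 points (f = 0.9) or 1.8 points (f = 0.7), by about 0.3 or 1.1 if half of the losses precede day 30, and by nothing if all do. Across the mortality levels tried, the upper bound runs from 0.3 to 3.4 points; only the largest is about as wide as the n = 300 half-width.

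Two stronger readings are tempting. One is that 30-day mortality will be overstated. The documents do not support it, since the sign turns on whether early deaths have complete records more often than known day-30 survivors do. The other is that the whole gap between the 5.3.1 rate and true mortality is due to 5.3.1. That holds only if nobody is lost before day 30, and early loss is plausible: discharge is put at 7 to 14 days, and section 9.2 says that sites follow patients differently. The point should be fixed, but it is not a flaw that invalidates the study.

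**What to change.** Use one rule in the synopsis (inclusion and follow-up rows), 5.3 and 5.3.1: all patients whose POLYTHESE surgery was at least one year before data extraction and who have not objected, whatever the length of follow-up available. The synopsis inclusion row also limits the indication to aneurysm or arterial disease, and 5.3.1 does not; say alike in every place whether that limit applies.

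Calculate 30-day mortality on all patients with known day-30 status. Report how many were lost before day 30 and how many between day 30 and 1 year. The handling of the latter for 1-year and later endpoints can be left to the SAP. Settle the wording before letters go out, since adding patients later means further letters as well as further charts.

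The cost is protocol wording and more charts with short follow-up. If enrolment stops at 300, the assumed losses leave 0.90 × 0.10 = 9% (27 patients) or 0.90 × 0.30 = 27% (81 of 300; 54 of 200 thoracic) without 1-year status. The 1-year confidence interval is then wider by a factor of 1/√0.91 = 1.05 or 1/√0.73 = 1.17. If extraction continues past 300, 1-year patency loses no information. Patients lost before day 30 remain uncounted, which is why their number should be reported.

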7.1. Performance endpoints

Primary performance endpoints are **primary patency rate at 1 year** after surgery using POLYTHESE®.

The others effectiveness endpoints are:

- Procedural success rate, defined as:
 - o Ability to use with no need for replacement by another device and,
 - o Effective vascular flow restoration after procedure and,
 - o In case of aneurysm, exclusion of aneurysmal portion after procedure.

PROTOCOL	2021-PT-01
TITLE:	Safety and Performance of POLYTHESE® vascular prosthesis
EFFECTIVE DATE:	1 July 2021

- Primary patency rate, defined as rate patency of the bypass graft without procedure or intervention of the conduit itself (except for occlusion)
- Primary assisted patency rate, defined as rate patency of the bypass graft with or without procedure or intervention of the conduit itself (except for occlusion) after device implantation
- Secondary patency, defined as rate patency of the bypass graft with or without procedure or intervention of the conduit itself for occlusion after device implantation
- Device Failure, defined as:
 - o Uncontrolled blood leakage from device
 - o Loss of structural integrity, e.g. rupture and/or exaggerated dilation (> 50 %)
 - o Occlusion of the device
 - o Total or partial replacement of the device required

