9.2. Data to collect

As mentioned previously considering study is retrospective and considering that every site can have different ways to follow their patients after surgery, data will be collected as much as possible in order to determine the clinical safety and performance.

The following data will be collected, when available according to participating site available data.

- **Identification and demographic data**

- Patient identification
- Indication and location of the treatment
- Location of the surgery
- Patients demographics
 - Year of birth
 - Sex
 - Mass
- Identification of implanting physician
- Name of the institution

- **Pre-operative data**

- Risks factors, such as hypertension, diabetes, coronary artery disease, hyperlipidaemia, tobacco use, obesity, anaesthesia risk and any cardiovascular risk factor.
- Summary of previous vascular interventions at the same or other relevant vascular sites, including non-surgical interventions and previously implanted vascular devices (e.g. stents, endovascular prostheses, surgically placed vascular grafts)
- Relevant medications
- Diagnostic criteria
 - Clinical assessment (e.g. non-invasive hemodynamic assessment);
 - Objective assessment (e.g. C.T. scanning, magnetic resonance imaging, ultrasonography, arteriography, duplex Doppler)

- **Operative data**

- Date of procedure
- Identification data for the vascular prosthesis including configuration (e.g. straight uniform or bifurcated) and diameter
- Information regarding the procedure:
 - Identity of native vessel treated

PROTOCOL	2021-PT-01
TITLE:	Safety and Performance of POLYTHESE® vascular prosthesis
EFFECTIVE DATE:	1 July 2021

- Details of anastomoses (e.g. type (end-to-end), location)
- Length of prosthesis implanted (if available)
- Adjunctive vascular procedures
- Relevant medication (e.g. heparin, other anticoagulants)
- Assessment of prosthesis function and mode of assessment if available (e.g. intraoperative angiography, intraoperative Doppler)
- Failure modes and adverse operative events
- **Post-operative data**
 - Interval of follow-up (e.g. discharge or 7 d to 14 d after surgery, 30 days, 6 and 12 months after surgery, up to 5 years for exploratory time points)
 - Date of follow-up visits
 - Summary of vascular interventions, including minimally invasive procedures
 - Clinical evaluation:
 - Clinical assessment (e.g. non-invasive hemodynamic assessment)

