9.4. Missing data

Some endpoints can be missing for some subjects. Endpoints proportions will be calculated on the number of non-missing observations. No imputation method is planned.

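### The protocol fixes 1-year primary patency as a proportion of non-missing observations without saying what settles 1-year status, so the rate can depend on which grafts were assessed

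*Protocol*

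**What the plan says.** The synopsis names the primary performance endpoint: "Primary patency rate at 1 year after surgery using POLYTHESE". Section 7.1 gives the definition: "Primary patency rate, defined as rate patency of the bypass graft without procedure or intervention of the conduit itself (except for occlusion". It states no method of assessment, no time window, no rule for events or images away from month 12, and no rule for death.

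Two places govern who enters. Section 5.3.1 requires "Patient has a minimum of 1-year post-operative follow-up data available, or complete data to death". Section 5.3 says that "all subjects with POLYTHESE® implanted for at least one year and have not objected to the collect of their data will be included". The first asks for a year of data and the second for a year since implantation. Neither asks for an assessment of the graft.

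Section 9.2 accepts that "every site can have different ways to follow their patients after surgery, data will be collected as much as possible", and adds: "The following data will be collected, when available according to participating site available data". Objective assessment of the prosthesis is one of the items collected on that footing.

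Section 9.4 sets the denominator: "Endpoints proportions will be calculated on the number of non-missing observations". No imputation is planned. The statistical design section (the first of two numbered 8.1) likewise leaves missing values out of denominators. It rejects multiple imputation because the data can be regarded as neither MCAR nor MAR.

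**The concern.** A complete-case proportion is generally unbiased only if the chance of being assessed is unrelated to graft status. The protocol uses the opposite premise to rule out imputation, then adopts the complete-case proportion with no bounds or sensitivity analysis named. In routine care, imaging prompted by symptoms would over-represent failed grafts and lower the rate. Early failures or deaths that were never re-assessed would raise it. The balance may differ by site and by surgical location, and section 5.3 lets one centre supply up to half of the subjects.

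There is a second gap. Primary patency, once lost, is not regained, so 12-month status often follows from a dated event before month 12 or an image after it. The protocol does not say that such evidence counts. At stake is whether the primary performance figure uses what the charts already show.

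**Working it through.** **Plan's own figure.** There is none to reproduce. The protocol gives no expected patency rate and no expected share of assessed grafts, and the minimum of 300 subjects (200 thoracic) rests on feasibility. The rates and assessment shares below are assumptions.

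**Step 1: two readings of section 9.4.**

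| Chart shows | Status settled by all dated evidence | Status read only at month 12 |
|---|---|---|
| Occlusion or qualifying intervention at month 4, no later image | Failure | Missing |
| Patent at month 18, no earlier occlusion or intervention | Patent | Missing |
| Patency lost, then death, both in year 1 | Failure | Missing |

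The text excludes neither reading. Section 7.1 also lists occlusion as a device failure. Under the right-hand reading, the first subject would be a device failure by 6 months and yet absent from 1-year patency.

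**Step 2: effect of selective assessment.** Let p be true patency, and let a1 and a0 be the shares of patent and failed grafts with a usable status. The reported rate is

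R = p·a1 / [p·a1 + (1 − p)·a0], which equals p when a1 = a0.

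Assume 300 subjects with 15 losses in year 1, so p = 285/300 = 95.0%.

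- Half of the patent grafts and 14 of 15 failures have a status: 285 × 0.5 = 142.5, and 142.5/(142.5 + 14) = 91.1%, or −3.9 points.
- 70% of the patent grafts and 5 of 15 failures have a status: 285 × 0.7 = 199.5, and 199.5/(199.5 + 5) = 97.6%, or +2.6 points.

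**Step 3: the confidence interval does not show it.** Clopper-Pearson 95% limits are 91.9% to 97.2% for 285/300. With 20% missing and the same observed rate (228/240) they are 91.4% to 97.4%. The interval hardly widens, while the shifts in Step 2 are about as large as its half-width.

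**Step 4: bounds.** With x patent among n assessed out of N, the full-cohort rate lies between x/N and (x + N − n)/N. Assuming about 95% patent among those assessed:

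| N | Without status | x/n | Lower | Upper |
|---|---|---|---|---|
| 300 | 10% | 256/270 | 85.3% | 95.3% |
| 300 | 20% | 228/240 | 76.0% | 96.0% |
| 300 | 30% | 200/210 | 66.7% | 96.7% |
| 200 (thoracic) | 30% | 133/140 | 66.5% | 96.5% |

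These are extremes, not expectations.

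**Step 5: classifying status better within a proportion is not enough.** Suppose every documented failure counts, but a graft counts as patent only if imaged at or after month 12. With all 15 failures in:

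- Half of the patent grafts imaged: 142.5/(142.5 + 15) = 90.5%.
- 70% imaged: 199.5/(199.5 + 15) = 93.0%.

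Both lie below 95.0%, and the first is further from it than the 91.1% of Step 2. To come within 1 point, 285s/(285s + 15) ≥ 0.94 requires s ≥ 14.1/17.1 ≈ 82% of patent grafts to be captured. A proportion also discards a graft seen patent at month 6 and not assessed again, which a time-to-event estimate keeps at risk up to that date.

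**The case against.** A reader might infer that section 9.4 restricts the rate to subjects assessed at month 12. It does not say so. It speaks of endpoints that may be missing, and a loss of patency documented at month 4 can be taken as a known endpoint. Nothing forbids using a month-18 image either. This objection stands: dropping such subjects is one plausible reading, not the stated rule.

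It can also be said that section 9.2 collects visit dates, interventions, graft assessments and dated events where available, that section 9.5 foresees derived variables, and that detail is left to the SAP. This stands in part. Deriving status from dated evidence could be settled in the SAP, but the complete-case denominator and the view that missingness is not random are already fixed in the protocol. Step 5 shows that the denominator remains a problem even under the more generous reading.

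The statistical design section already tabulates missing observations as a separate category and plans analyses by surgical location, so part of the reporting exists. What is absent is a breakdown by site and any bounds.

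Finally, the study is descriptive, tests no hypotheses, and openly states that "every site can have different ways to follow their patients after surgery". Nor is the criterion in 5.3.1 wrong in itself: requiring a 12-month image for entry would select subjects in its own way. Both remarks stand, and the remedy therefore belongs in the endpoint definition and the analysis.

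**Conclusion.** The point holds as a weakness in how the primary performance rate is defined and estimated. The protocol prescribes a complete-case proportion, says that missingness is not random, requires no graft assessment, and does not say that evidence before or after month 12 settles the 1-year status. Following it can therefore bias 1-year patency.

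Direction and size are unknown. The range of −3.9 to +2.6 points illustrates what selective assessment could do with a true rate of 95.0% and the shares assumed in Step 2; it is not an estimate for this study. Two stronger conclusions are tempting but unsupported: that the protocol orders subjects of known status to be dropped, and that the rate is uninterpretable. The first adds words to section 9.4. The second goes too far for a descriptive study whose actual share of unassessed grafts is not given. The change should still be made, because this is the primary performance endpoint and the data needed are already to be collected where available.

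**What to change.** In sections 7.1 and 9.4 of the protocol, carried into the SAP:

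1. Count any occlusion or qualifying conduit intervention documented on or before day 365 as loss of primary patency, whether or not a 12-month assessment exists, and including subjects who later died.
2. Let a later assessment that shows a patent graft, with no earlier occlusion or intervention, establish patency at 12 months.
3. Replace the non-missing proportion for patency at 30 days, 6 months and 1 year with a time-to-event estimate: Kaplan-Meier with censoring at the last graft assessment. State whether death before loss of patency is censored or treated as a competing event.
4. Report the number without 12-month status by location and by site, with best-case and worst-case bounds as a sensitivity analysis.

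No eligibility change is needed for this purpose. The cost is wording and some extra programming on data already to be collected where available. There are two downsides. Censoring at the last assessment may still be informative where imaging follows symptoms, so item 3 does not remove the problem alone and the bounds in item 4 are needed. The reported rate may also be less favourable.
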